Target Population and sample size	The patients selected for this PMCF activity will be adults (over 18 years) requiring microsurgical reconstructive procedures applied to arterial, venous, neural or lymphatic anastomosis. The planned minimum sample size is 402 patients to ensure lower 95% confidence limit for the Primary Endpoint. A drop out rate of 5% will allow to include a total of 420 subjects. All subjects will be enrolled and followed in at least 3 EU centres until the sample size is reached.

**RASM
POST MARKET CLINICAL FOLLOW-UP
STUDY
Synopsis**

CDC-00031
Rev. 03
Page: 2/4

Duration of Study	Each enrolled subject will be followed through the first 30±7 days post-operatively or 24 weeks post-operatively (according to the procedures) per the follow-up schedule reflecting the standard of care.
Primary Endpoint	The primary endpoint will be defined as the ability to complete the surgical task with Symani as intended by the surgeon. This endpoint will be referred to as “Procedure Robotic Success”.
Secondary Endpoints	
The main secondary endpoint will be the rating of the surgeon experience of robot usability, which will be assessed using a questionnaire.
 
Further secondary endpoints will be assessed regarding the clinical outcome of the procedures. These criteria will differ depending on the procedure performed being a replantation, free flap surgery, lymphatic surgery or other.
 
Replantations
 
• Time for each anastomosis execution and warm ischemia time (minutes)• Intraoperative need to redo the anastomosis (yes or no)• Postoperative need to redo within 7 days (complication and need to return to the operating room to explore anastomosis: yes or no)• Complications• Replantation Failure or Loss (subsequent amputation) 
Free Flaps
 
• Time for each anastomosis execution and warm ischemia time (minutes)• Intraoperative need to redo the anastomosis (yes or no)• Postoperative need to redo within 7 days (complication and need to return to the operating room to explore anastomosis: yes or no)• Complications• Flap Failure or Loss (yes or no) 
Lymphatic Surgery
 
• Time for each anastomosis execution (in minutes)• Intraoperative need to redo based on ICG Patency (yes or no)• Postoperative need to redo based on ICG Patency (yes or no)• Complications• Limb volume reduction

**RASM
POST MARKET CLINICAL FOLLOW-UP
STUDY
Synopsis**

CDC-00031

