2.1.3.1 Primary effectiveness endpoint – Procedure Robotic Success

Form R or Anastomosis Data Form will be completed for each anastomosis. If the answer to the question 'How did you intend to perform this anastomosis' is 'Robotic' then the anastomosis is included for this endpoint.

The endpoint will be derived for each anastomosis using the question "Did you experience any system technical issues resulting in unplanned return to conventional suturing".

If the response is 'No' and the number of robotic sutures is > 0 or the number of robotic redo sutures is > 0, the anastomosis will be classified as 'intra-operative change from robotic to manual' = 'no'.

If the response is 'yes' anastomosis will be classified as intra-operative change from robotic to manual = 'yes'.

If there is no response to the question the anastomosis classification will be missing.

If the planned approach was manual the result will be N/A

The unit of analysis for this endpoint is the anastomosis.

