2.1.3.2.3 Intraoperative need to redo the anastomosis (yes or no)

Castor' and Dendrite's anastomosis form has a question 'timing of anastomosis', with the options 'first attempt' and 'subsequent attempt'. Subsequent attempt is a redo form.

Redo forms will be 'aligned' with first attempt forms by matching anastomosis type (free flap, replantation) according to the form completed and with surgery type by matching the responses to the questions:

Side, vessel type and vessel diameter.

Sponsor: MMI Product: Symani system for microsurgical anastomosis Study: PRIMO	
Statistical Analysis Plan Final 22 November 2024	

For lymphatic surgery matching will be done using type (lymphatic anastomosis form completed), type of anastomosis and vein diameter.

Any anastomosis which has at least one redo form will be classified as redo="yes".

Any anastomosis which does not have a matching form for subsequent attempt will be classified as redo="No".

If there are subsequent attempt forms which do not directly align with a first attempt form, this will be resolved by clinical review so all subsequent attempt forms are aligned with a first attempt form.

For this analysis, the anastomosis is the unit of analysis.

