2.1.3.2.4 Post-operative need to redo the anastomosis within 7 days (yes or no)

The need for a re-operation (yes/no) is recorded on several forms, namely Castor operation data forms contain the question 'Any post-operative need to redo?' and all post-surgery visit forms (visit 1 (24 hours), visit 2 (4 days post-surgery), visit 3 (14 days post-surgery) and visit 4 (30 days post-surgery for free flaps and replantations, 24 weeks post-surgery for lymphatic operations) and the unplanned visit form have the question "Postoperative need to redo?".

Note, the derivation of this endpoint is at the procedure level. Re-operation forms are by procedure (free flaps, replantation, lymphatic surgery) and will be 'aligned' to the index operation of the same type.

If, for that procedure, the answer to any of the questions above is yes, there should be a re-operation form for that procedure

The date of re-operation is recorded on the re-operation form.

The time (in days) to re-operation will be determined as:

Date of reoperation – date of index operation.

If the time to re-operation is ≤ 7 days then the patient will be classified as reoperation within 7 days = Yes.

If there are no re-operation forms where the time to re-operation is ≤ 7 days then the procedure will be classified as re-operation within 7 days = No.

If there are no re-operation forms (and ALL questions above are No, for need for a re-operation) for that procedure type, then re-operation within 7 days = No.

If any of the questions suggest there was a re-operation but there is no accompanying re-operation form then the following approach will be used.

- If the answer to re-operation needed is "yes" on the index operation form or the form for visit 1 (24 hours) or visit 2 (4 days) is Yes, then re-operation = Yes.

Sponsor: MMI Product: Symani system for microsurgical anastomosis Study: PRIMO	
Statistical Analysis Plan Final 22 November 2024	

- If the answer for re-operation on the unplanned visit form is “yes”, then if the date of the unplanned visit is within 7 days of the date of the index procedure, then re-operation = “yes”.
- If a clinical review of available data suggests there was a re-operation within 7 days then re-operation = “yes”.
- In other circumstances re-operation within 7 days will be missing.

This analysis is at the procedure level.

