2.2.2 Effectiveness populations

2.2.2.1 Full Analysis Set (FAS)

The FAS will comprise patients in the All Enrolled Set for whom a robotic anastomosis has been performed. A robotic anastomosis is defined as having received at least 1 robotic suture as part of a study procedure. To assist in this determination, for the index procedure, for each anastomosis attempted, the number of robotic sutures will be classified as follows from CRF data:

0 (zero) robotic sutures

≥ 1 robotic sutures (minimum requirement for inclusion in the Safety Analysis Set (SAS) and the FAS)

If the number of robotic sutures is missing, then the anastomosis will be classified as robotic provided the following criteria are met:

The response to the question 'How did you intend to perform the anastomosis?' = 'Robotic **and**

The response to the question "Did you experience any system technical issues resulting in unplanned return to conventional suturing"? = "No".

If at least one anastomosis is classified as robotic (as defined above) the patient will be considered treated robotically and will be included in the FAS for assessment of effectiveness.

The FAS will form the basis of all summarization and analysis of effectiveness variables. However, for each effectiveness variable, the data summary and analysis will only include patients that have non-missing data for the effectiveness outcome being analyzed. The number of patients included in the analysis/summary will be clearly indicated in each tabular presentation.

2.2.2.2 Subpopulations of the FAS.

Two distinct sub-populations will be defined based on the FAS.

- The prospective patient sub-population

Sponsor: MMI Product: Symani system for microsurgical anastomosis Study: PRIMO	
Statistical Analysis Plan Final 22 November 2024	

- The retrospective patient sub-population.

All summaries and analyses will be presented using all data combined and by sub-population.

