2.4.4.2.2 Anastomosis execution time

Robotic usage time, manual suture time and total suture time are derived as described in section 2.1.3.2.2. This analysis is at the anastomosis level.

For each surgery type, results for each variable will be summarized using descriptive statistics overall and by subpopulation (prospective/retrospective) and by recipient site. The denominator for all calculations will be the number of anastomoses.

For each surgery type, a general linear mixed model (GLMM, using SAS proc mixed) will be fitted with time as the outcome and recipient site/location and subpopulation as fixed effects. Procedure number (within a surgery type) and anastomosis number (within a procedure) will be included as random terms to acknowledge the dependence in the data (see note above). For each type of surgery, from the model the adjusted mean time will be obtained, with 95% confidence limits, overall and by recipient site and subpopulation. Model 3.

For replantations an additional fixed effect for procedure type (free or nerve) will be included and results obtained by procedure type (free/nerve). Model 3a.

Separate models will be fitted for robotic time, manual time and total time for each surgery type.

2.4.4.2.3 Intra-operative need to redo the anastomosis.

As per section 2.1.3.2.3 each anastomosis for each patient in the FAS will be assigned to 'Yes' or 'No' for intra-operative redo. This represents a binary outcome. The analysis of this variable is at the anastomosis level.

Summary and analysis will be as described for the primary effectiveness endpoint (model 1/1a).

Sponsor: MMI Product: Symani system for microsurgical anastomosis Study: PRIMO	
Statistical Analysis Plan Final 22 November 2024	

2.4.4.2.4 Post-operative need to redo within 7 days.

As per section 2.1.3.2.4 each patient in the FAS will be assigned to 'Yes' or 'No' for post-operative redo within 7 days for each surgery type. This represents a binary outcome. The analysis of this variable is at the procedure level.

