2.4.4.3.2 Intraoperative anastomosis patency

As per section 2.1.3.5.2, each robotic anastomosis conducted on each patient in the FAS during their index procedure will be assigned to 'Yes' or 'No' for intraoperative anastomosis patency. This represents a binary outcome at the anastomosis level.

Methods for summarization and analysis will be as described for the primary effectiveness endpoint (Model 1/1a).

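### Intra-operative redo and total anastomosis time pool planned-manual with robotic anastomoses, and lymphatic post-operative redo is cut at 7 days although its definition has no time limit

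*SAP*

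**What the plan says.** **Who enters the analysis.** FAS membership (SAP 2.2.2.1) is decided per patient: "If at least one anastomosis is classified as robotic (as defined above) the patient will be considered treated robotically". SAP 2.1.2 records the intended approach, manual or robotic, for each anastomosis, so mixed patients are expected.

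**Endpoints that separate the approaches.** For the primary endpoint, 2.1.3.1 states: "If the planned approach was manual the result will be N/A". For patency, 2.4.4.3.2 covers only robotic work: "each robotic anastomosis conducted on each patient in the FAS during their index procedure will be assigned to" Yes or No.

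**Endpoints that do not.** For intra-operative redo, 2.1.3.2.3 never uses intent: "Any anastomosis which does not have a matching form for subsequent attempt will be classified as redo" = No. The analysis in 2.4.4.2.3 then says "As per section 2.1.3.2.3 each anastomosis for each patient in the FAS will be assigned to" Yes or No. For execution time, 2.1.3.2.2 adds robotic and manual minutes for each anastomosis, and 2.4.4.2.2 says "The denominator for all calculations will be the number of anastomoses". Robotic, manual and total time are modelled separately.

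**Lymphatic post-operative redo.** The protocol synopsis lists, for lymphatic surgery, "Postoperative need to redo based on ICG Patency (yes or no"), and SAP 1.3.1 repeats it. In both lists the 7-day limit is attached only to replantations and free flaps. SAP 2.1.3.2.4 has one rule for all three surgery types: if no re-operation form falls within the window, "then the procedure will be classified as re-operation within 7 days = No". SAP 2.4.4.2.4 models that 7-day outcome for each surgery type.

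**The concern.** **(a)** A patient with one robotic and two manual anastomoses contributes three units to the redo rate and to mean total time. Readers will take these as results for Symani, but they also depend on how much manual work was done alongside. That share may differ by surgery type, recipient site, surgeon and cohort, so prospective and retrospective results could differ through case mix alone. Neither the redo model nor the time model has a term for intended approach, so adjustment does not separate the two.

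**(b)** The lymphatic endpoint as analysed is not the one defined. It replaces need to redo on ICG patency with re-operation within 7 days, for patients followed for 24 weeks. Section 1.5 of the SAP, which lists departures from the protocol, does not mention it.

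**Working it through.** **No plan figure to reproduce.** The documents give no expected redo rate, no execution time and no share of planned-manual anastomoses. The power statement in SAP 1.7 concerns the primary endpoint only. All rates, times and shares below are therefore assumptions.

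**Step 1: which anastomoses count.**

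| Endpoint | Derivation | Planned-manual anastomoses |
|---|---|---|
| Robotic success | 2.1.3.1 | Not applicable |
| Patency | 2.1.3.5.2, 2.4.4.3.2 | Analysis names robotic anastomoses only |
| Intra-operative redo | 2.1.3.2.3 | Included; No unless a redo form matches |
| Total time | 2.1.3.2.2 | Included |
| Robotic time | 2.1.3.2.2 | Not stated whether 0 or missing |

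**Step 2: effect on redo.** Let *m* be the planned-manual share. Crude reported rate = (1 − *m*) × robotic rate + *m* × manual rate, so the shift from the robotic rate is *m* × (manual − robotic).

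| *m* | Robotic 10%, manual 3% | Robotic 5%, manual 10% | Both 5% |
|---|---|---|---|
| 10% | 9.3% | 5.5% | 5.0% |
| 25% | 8.25% | 6.25% | 5.0% |
| 40% | 7.2% | 7.0% | 5.0% |
| 50% | 6.5% | 7.5% | 5.0% |

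At *m* = 40%: 0.6 × 10 + 0.4 × 3 = 7.2, and 0.6 × 5 + 0.4 × 10 = 7.0. Two quite different robotic rates, 10% and 5%, give almost the same reported figure. In the first scenario, a cohort with 10% planned manual and one with 50% would differ by 9.3 − 6.5 = 2.8 points with identical performance.

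**Step 3: effect on time.** Assume a mean of 25 minutes for robotic anastomoses and 15 for manual ones.

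- Total time at *m* = 10%, 25%, 40%, 50%: 24.0, 22.5, 21.0, 20.0 minutes, against 25 when restricted (at 40%: 0.6 × 25 + 0.4 × 15 = 21).
- Robotic time, if planned-manual anastomoses carry 0: 22.5, 18.75, 15.0, 12.5 minutes against 25. If they are missing they drop out and nothing shifts.
- Manual time is not offered as a Symani result.

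**Step 4: a lymphatic redo on day 20 under 2.1.3.2.4.**

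- With a re-operation form dated day 20: 20 > 7, so the result is No.
- With no re-operation form and need for redo noted only at a visit after day 7: missing, unless clinical review places it within 7 days. Missing outcomes are excluded under 2.5.2.
- ICG patency is used in neither 2.1.3.2.3 nor 2.1.3.2.4.

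The window is 7 of 24 × 7 = 168 follow-up days, or 4.2%. That measures window length, not the fraction of redos missed.

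**The case against.** - **The FAS sentence alone does not show pooling.** SAP 2.4.4.1 uses nearly the same sentence for the primary endpoint, where planned-manual anastomoses are removed, and 2.4.4.2.3 says redo is analysed as the primary is. This is right about the sentence. But the primary's exclusion sits in its derivation, not in its model, and redo points to its own derivation, which has no exclusion. Borrowing the model brings none with it.
- **Pooling may be intended.** The endpoint lists describe clinical outcomes of the procedures, with no robotic qualifier, and the SAP plans no hypothesis test on them. This stands in part: an all-anastomoses summary is legitimate if labelled as such. It does not describe the device, which is what the study objective concerns.
- **The two precedents differ.** The primary filters on intent; patency refers to robotic anastomoses, which 2.2.2.1 defines by sutures placed. This is true, so a choice is needed. Intent is preferable because a rule based on sutures placed could drop attempts abandoned before any robotic suture.
- **Robotic time is probably unaffected.** SAP 2.2.3.1 treats a recorded robotic time as the sign of an attempt, which suggests it is blank for manual work. This is plausible, but the coding rule is not written down.
- **Late lymphatic redos are visible elsewhere.** Adverse events are recorded to 24 weeks for LVA procedures (2.1.5) and listed (2.4.6.1). The 30-day re-operation analysis (2.4.6.2.4) includes lymphatic procedures, although the source forms in 2.1.5.1.4 are free-flap and recipient-site forms. This stands: the event drops out of the endpoint, not necessarily out of the study.

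**Conclusion.** The point holds in both parts, as an inconsistency that should be corrected.

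**(a)** As derived, the intra-operative redo rate and mean total time pool planned-manual with robotic anastomoses. The shift equals the manual share times the difference between approaches. In the assumed scenarios it ranges from a fall of 3.5 points (10% to 6.5%) to a rise of 2.5 points (5% to 7.5%), and is nil if the approaches do not differ. A reader might infer that pooling flatters Symani, or that every reported time is contaminated. The documents support neither: they give no rates by approach and no manual share, and robotic time is affected only if planned-manual anastomoses are coded 0.

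**(b)** Lymphatic post-operative redo is defined without a time limit and on ICG patency, but derived as re-operation within 7 days, undeclared. A redo after day 7 with a re-operation form is No for this endpoint. A reader might infer that late lymphatic failures vanish from the study; adverse-event reporting to 24 weeks means they need not.

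**What to change.** **(a)** In 2.1.3.2.3/2.4.4.2.3 and 2.1.3.2.2/2.4.4.2.2:

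- Restrict the main redo, robotic-time and total-time analyses to anastomoses whose intended approach was robotic, the rule already in 2.1.3.1. For redo, take intent from the first-attempt form.
- Tabulate planned-manual anastomoses separately.
- Set robotic time to not applicable, never 0, for planned-manual anastomoses.

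Intent is already recorded, so this costs SAP wording. The downside is fewer anastomoses and wider intervals; the reduction equals the manual share, which the documents do not give.

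**(b)** Reconcile 2.1.3.2.4 and 2.4.4.2.4 with the protocol synopsis and SAP 1.3.1. Derive the lymphatic endpoint as need to redo based on ICG patency over the 24-week follow-up, from the lymphatic visit and re-operation forms. Keep the 7-day rule for free flaps and replantations. Report any 7-day lymphatic result as additional and list it in section 1.5. Re-operation dates and the redo question at each visit are already collected. The documents do not say which field holds a post-operative ICG result, so the SAP should name it, or state the limitation if none exists.

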2. STATISTICAL AND ANALYTICAL PROCEDURE

The study has a hierarchical structure as follows:

- There are three types of surgery: free flaps, replantations, and lymphatic. A patient may have more than one type of surgery (e.g flap and replantation).
- Within a type of surgery, e.g. free flaps, a patient may have more than one procedure during an operation.
- Within each procedure, anastomoses are performed. More than one anastomosis may be performed within a procedure.

For the purpose of this SAP, endpoints may be defined at any of these levels, i.e. patient, surgery type, procedure within a surgery type, anastomosis within procedure. This hierarchy is described in Figure 1. The unit of analysis for each endpoint will be clearly defined in this SAP.

Sponsor: MMI Product: Symani system for microsurgical anastomosis Study: PRIMO	
Statistical Analysis Plan Final 22 November 2024	

Figure 1 hierarchy of dependence in the endpoint data.

Level			
Surgery type within patient	Free flap	Replantation	Lymphatic
Procedure within surgery type	FF1, FF2, FF3 etc	R1, R2, R3 etc	LVA1, LVA2, LVA3 etc
Anastomosis within procedure	FF1A1, FF1A2, FF2A1, FF2A2, FF3A1, FF3A2, etc	R1A1, R1A2, R2A1, R2A2, R3A1, R3A2, etc	LVA1A1, LVA1A2, LVA2A1, LVA2A2, LVA3A1, LVA3A2, etc

In addition to this hierarchical structure regarding the initial attempt, for a particular anastomosis, there may be the need for an intraoperative redo within the same operation (a secondary endpoint), or the need for a re-operation on a subsequent date (a secondary endpoint). This patient flow is described in Figure 2.

[figure not shown]

Sponsor: MMI Product: Symani system for microsurgical anastomosis Study: PRIMO	
Statistical Analysis Plan Final 22 November 2024	

Figure 2. Patient flow through study procedures

Note. Procedure = flap or replantation or lymphatic. [1] There may be > 1 procedure done. A second procedure may be the same type as procedure 1 (e.g 2 flaps procedures) or may be different. The figure suggests 2 procedures (due to space limitations) but there may be > 2 procedures.

Sponsor: MMI Product: Symani system for microsurgical anastomosis Study: PRIMO	
Statistical Analysis Plan Final 22 November 2024	

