2.1.3.3 Secondary Effectiveness Endpoints - Free Flap and Replantation

2.1.3.3.1 Ischemia time

Warm ischemia time is captured directly on the operation CRF (for free flaps and replantations).

2.1.3.3.2 Free flap failure or loss at discharge/replantation failure or loss (subsequent amputation).

This endpoint only refers to flap procedures or replantations.

The unit of analysis is the flap/replantation, i.e. at the procedure level.

Separate variables will be derived for flaps and replantations.

For each flap, Dendrite’s form H and Castor’s Free Flap Operation Visit operation visit: Operation Data Forms record the answer to the question ‘Flap survival at recipient site at discharge’, with options ‘100% - complete survival’, ‘partial survival’, ‘zero survival’, ‘buried flap’ or ‘unknown’. In Dendrite, the same form is used for replantations, so if the procedure is replantation, then the question will be interpreted as ‘Replantation survival at discharge’.

Each flap will be classified as ‘loss/failure’ = yes if the response to the question is ‘zero survival’ and loss/failure = ‘no’ if the response is ‘100% complete survival’ or ‘Partial survival’. If the response is ‘buried flap’ or ‘unknown’ the response will be missing.

For replantations the options are:

Yes, No, partial failure, not applicable

Sponsor: MMI Product: Symani system for microsurgical anastomosis Study: PRIMO	
Statistical Analysis Plan Final 22 November 2024	

Each replantation will be classified as ‘loss/failure’ = yes if the response to the question is ‘yes’ and loss/failure = ‘no’ if the response is No or ‘Partial failure’. If the response is not applicable the response will be missing.

For both variables, if the question is not answered the variable will be missing.

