The analysis models described below (where the unit of analysis is not the patient), allows for the most complex structure of data dependence/repeated measures; namely recipient site/location will be included as a fixed effect (as noted above), but procedure number (within type) and anastomosis number (within procedure for analyses where the unit of analysis is at the anastomosis level) will be included as random terms as required to acknowledge the repeated measures in the data. A decision will be made on production of the initial summary table on the level of complexity required for each analysis. Note, for all endpoints (unless otherwise specified) separate models will be fitted for each surgery type and all models for replantations will include the additional fixed effect of procedure type (free or nerve).

Sponsor: MMI Product: Symani system for microsurgical anastomosis Study: PRIMO	
Statistical Analysis Plan Final 22 November 2024	

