For each surgery type (replantation, free flap or lymphatic surgery) stratified frequency tables will be presented stratified by subpopulation (prospective/retrospective) and recipient site/location. For replantations an additional stratum, procedure type (free or nerve) will be included. The denominator is the number of procedures. The proportion of procedures needing a post-operative redo by stratum and overall for each surgery type will be presented with 95% confidence limits. Results will also be presented on a forest plot

For each surgery type a generalized linear mixed model (GLMM) will be used to estimate the percentage of procedures needing a post-operative redo within 7 days. In SAS, PROC GLIMMIX will be utilized to analyze the data. Recipient site/location and subpopulation (prospective/retrospective) will be included as fixed effects, and surgeon as a random effect. Procedure number (within a patient) will be included as a random term to acknowledge the dependence in the data (namely that each patient may have > 1 procedure and any number may require post-operative redo). From the model the adjusted rate of post-operative redo can be obtained, with 95% confidence limits, for all procedures combined and by procedure type and subpopulation. Model 4.

For replantations, an additional fixed effect of procedure type (free nerve) will be included and results obtained by type. (Model 4a).

If most patients have only one procedure for a given surgery type, then the model will be simplified and the random term for procedure number will be dropped.

2.4.4.2.5 Warm ischemia time (flap and replantations only).

Warm procedure time (see section 2.1.3.3.1 for derivation) will be summarized and analyzed as described for anastomosis time.

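### Warm ischemia time comes from the operation form, one level above the anastomosis, but is sent to an anastomosis-level analysis; its unit should be the procedure

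*SAP*

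**What the plan says.** Warm ischemia time is a protocol secondary endpoint for free flaps and for replantations. On its source, SAP 2.1.3.3.1 says: "Warm ischemia time is captured directly on the operation CRF (for free flaps and replantations". Suturing times come from a different form, completed for each anastomosis (SAP 2.1.3.2.2).

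The analysis of warm ischemia time in SAP 2.4.4.2.5 is a single cross-reference: it "will be summarized and analyzed as described for anastomosis time". The method referred to, in SAP 2.4.4.2.2, states:

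- Unit: "This analysis is at the anastomosis level".
- Denominator: "The denominator for all calculations will be the number of anastomoses".
- Model 3: "Procedure number (within a surgery type) and anastomosis number (within a procedure) will be included as random terms".
- Output: "the adjusted mean time will be obtained, with 95% confidence limits".

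SAP section 2 promises: "The unit of analysis for each endpoint will be clearly defined in this SAP". Neither 2.1.3.3.1 nor 2.4.4.2.5 gives a unit for warm ischemia time, and its level and analysis cells in Appendix 1 are empty as the table reads. The neighbouring flap-loss endpoint is set explicitly at the procedure level (SAP 2.1.3.3.2 and 2.4.4.2.6).

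**The concern.** The variable and the method sit at different levels of the SAP's own hierarchy. A procedure may contain several anastomoses, so a value recorded above the anastomosis has no natural place in an analysis whose rows are anastomoses. Two programmers could follow the same sentence and produce different results. One would copy each ischemia time onto every anastomosis row. The other would keep one row per procedure and ignore the denominator and the anastomosis term. They would report a different n, possibly a different mean, and different confidence limits for a protocol secondary endpoint. A pre-specified plan should rule that out.

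**Working it through.** The documents give no mean, SD or target precision for warm ischemia time and no number of anastomoses per procedure (k). SAP 1.7 says the number per patient was unknown at design. There is therefore no plan figure to reproduce, and every input below is an assumption. I also assume one ischemia value per flap or replantation. The operation form implies this, but the case report forms are not among the documents.

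**1. Literal reading: count and mean.** Let s_k be the share of procedures with k anastomoses and m_k their mean time.

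- Rows per procedure = Σ s_k·k
- Mean by procedure = Σ s_k·m_k
- Mean by row = Σ s_k·k·m_k / Σ s_k·k

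Assume shares of 20%, 60% and 20% for k = 1, 2, 3, with means of 50, 60 and 80 min.

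- Rows per procedure: 0.2 + 1.2 + 0.6 = 2.0, so the reported n doubles.
- By procedure: 10 + 36 + 16 = 62 min.
- By row: (10 + 72 + 48) / 2.0 = 65 min.

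A milder case has half the procedures at k = 2 (mean 50) and half at k = 3 (mean 65). The mean is 57.5 by procedure and (2×50 + 3×65)/5 = 59.0 by row. If ischemia time is unrelated to k, the expected mean does not move, but n is still wrong.

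**2. Literal reading: limits if the copied rows were treated as independent.** With k copies per procedure, the standard error is multiplied by 1/√k, and nominal 95% limits cover 2Φ(1.96/√k) − 1.

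| k | SE ratio | Coverage |
|---|---|---|
| 1 | 1.00 | 95.0% |
| 1.5 | 0.82 | 89.0% |
| 2 | 0.71 | 83.4% |
| 3 | 0.58 | 74.2% |
| 4 | 0.50 | 67.3% |

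A simulation (100 procedures, mean 60, SD 20 min, 4,000 runs) gave 82.1% for k = 2 and 73.2% for k = 3. With one row per procedure it gave 94.3% to 94.4%. Mean interval widths were 5.5 min (k = 2) and 4.5 min (k = 3) with copies, against 7.9 min by procedure.

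**3. Literal reading: what Model 3 does with copies.** Model 3 does not treat rows as independent, because it has a procedure term. A simplified version (intercept plus a random procedure effect) shows the behaviour.

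- *Near-copies* (small noise, SD 0.5 min, added): the fit returns the procedure-level standard error. It is 2.06 against a naive 1.45 at k = 2, and 1.94 against 1.12 at k = 3. These limits are not too narrow.
- *Exact copies*: the within-procedure sum of squares is zero. Take m procedures, N = km rows, between-procedure sum of squares SSB, and ψ as the ratio of procedure to residual variance. The profiled residual variance is k·SSB / [(1 + kψ)(N − 1)], and the standard error of the mean is √[SSB / (m(N − 1))] for every ψ. That is the naive value. The REML log-likelihood has no maximum: in one k = 2 data set it rose from −672.3 at ψ = 0 to 283.4 at ψ = 10⁸. One mixed-model routine reported convergence at the naive standard errors (1.45 and 1.12). A moment estimator on copied data gave the procedure-level value (1.76 against a naive 1.24 at k = 2). Other software may simply fail.

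**4. Alternative reading: one row per procedure.** Repetition disappears, but the denominator sentence in 2.4.4.2.2 is then false for this endpoint. An anastomosis effect with one observation per level is also indistinguishable from the residual.

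**The case against.** The best defence is that no sentence in the SAP tells anyone to copy ischemia times onto anastomosis rows. SAP 2.4.4 brings in random terms as needed and ties anastomosis number to analyses run at that level. SAP 2.1.3.2.2 includes a procedure-level summary of suturing time, and SAP 2.4.1 requires each table to show its unit and its non-missing count. A sensible analyst could take the cross-reference to mean the same kind of model with one row per procedure. This stands as a plausible reading. It does not rescue the text, because under it the stated denominator and one random term are still wrong.

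A reader might infer that the limits will be too narrow. The documents do not support that as a certainty. The planned descriptive statistics for continuous variables carry no limits (SAP 2.4.1). The only planned limits come from Model 3, whose procedure term can absorb repeats. The coverage table in the working describes an analysis that the SAP does not plan. It would arise only by one of two routes. In the first, the procedure term is removed under SAP 2.4.4, where "A decision will be made on production of the initial summary table on the level of complexity required for each analysis". In the second, a degenerate fit is accepted despite the model checking in SAP 2.5.6.

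A reader might also infer that the nerve stratum in Model 3a does not belong here because nerve procedures have no ischemia time. No passage says so. If no value is recorded, SAP 2.5.2 already leaves the record out.

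The empty Appendix 1 cells carry limited weight, since tables may have been damaged in text extraction. The point does not depend on them.

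**Conclusion.** The concern holds as a mis-specified rule: the cross-reference gives warm ischemia time a unit and denominator that do not match how it is recorded. Taken literally, it inflates n and gives more weight to procedures with more anastomoses. It also leaves Model 3 without within-procedure variance, so the fit may fail, and the limits may be too narrow only under the two conditions named above. Taken charitably, part of the method still does not apply.

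The size is illustrative only. In the two assumed scenarios the mean shifts by 3.0 and 1.5 minutes, and with k = 1 throughout nothing changes. The endpoint has no hypothesis, threshold or comparator, so no trial conclusion turns on it. The correction should still be made, because the rule as written does not give a single reproducible result.

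**What to change.** In SAP 2.4.4.2.5, replace the cross-reference with a stated analysis, and complete the Appendix 1 row to match:

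- Unit: the procedure, with one record per flap or replantation. The denominator is the number of procedures with a recorded value.
- Model: a normal mixed model, fitted separately for flaps and replantations. Recipient site and subpopulation are fixed effects, plus procedure type for replantations. Surgeon is random, and patient is random where a patient has more than one procedure.
- Drop the anastomosis term. With one row per procedure, procedure number within patient also identifies a single row, so patient is the term that carries the dependence.
- Procedures with no recorded ischemia time, including any nerve procedures, are left out under SAP 2.5.2 and counted as missing in the table.
- Correct *Warm procedure time* in 2.4.4.2.5 to *Warm ischemia time*.

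The cost is a few lines of SAP text and one table row, with no new data. Compared with the literal reading, the reported n will be smaller. The limits will reflect the number of procedures actually observed.
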